# 8.3.7 Exploratory Efficacy Analyses

The exploratory efficacy endpoints are fully described in Section 8.1.4. All exploratory efficacy endpoints that involve a proportion of responders will be analyzed using methods similar to what was described for the HDSM-Ax-7 co-primary endpoint. For each endpoint, a logistic regression model will be generated using planned covariates of treatment, baseline parameter, and analysis center. For the composite endpoints, both baseline HDSM-Ax and GSP will be included as covariates.

All other exploratory endpoints that involve a change from baseline to a single timepoint for a continuous variable will be analyzed using methods similar to what is described for the GSP co-primary endpoint. For each endpoint, an ANCOVA model will be generated with fixed effects for treatment, baseline parameter, and analysis center.

Change in PGI-S from baseline and PGI-C score (only collected at Day 43) will be analyzed using a Cochran-Mantel Haenszel (CMH) test for ordinal data to compare the treatment arms at each visit.

All exploratory efficacy analyses will be based on available data and missing GSP and HDSM-Ax EOT data imputed per Section 8.2.1. HDSM-Ax-11 will be calculated in the same manner as HDSM-Ax-7 at EOT, where the mean is derived from imputed sub-items for the EOT score. In addition, all continuous parameters will be summarized by visit on the ITT population.

Data in the analysis of rank-based GSP change from baseline to each timepoint will be ranked in the same manner as that of the co-primary GSP endpoints (Section 8.3.2).

Proportion of subjects achieving 1- and 2-point improvement from baseline in HDSM-Ax-7 and HDSM-Ax-11 will be plotted at each timepoint. Similar plots will be generated for proportion of subjects achieving 50% and 70% reduction in GSP from baseline at each timepoint and for the secondary composite endpoints. Plots will be generated for change from baseline for continuous measures over time.

In addition, a summary table of frequency of missing measurements at each visit will be generated for GSP and HDSM-Ax-7, separately.

All secondary and exploratory efficacy endpoints will be analyzed for both the ITT and PP populations. The co-primary endpoint primary analyses will also be analyzed for the PP population as an exploratory analysis. Analyses completed on the PP population will not be multiply imputed. The PP population is a completers population and analyses based on this population will use observed data. P-values for exploratory efficacy endpoints will be provided for descriptive purposes only and no formal hypothesis testing will occur.

#### 8.4 Examination of Subgroups

While the study is not powered to show efficacy for pre-defined subgroups, the coprimary efficacy end points will be further analyzed by subgroups of interest . All pvalues from the subgroup tables will be of an exploratory nature, as no formal hypothesis testing will occur.

The primary analyses for the primary endpoints (see sections 8.3.1 and 8.3.2) will be repeated for the ITT population for the following subgroups:

- Age group: < 17 years,  $\ge 17$  to 30 years,  $\ge 31$  years.
- Gender: male, female.
- Ethnicity: Hispanic or Latino, Not Hispanic or Latino or not reported.
- Race: white, non-white or not reported.

Race and ethnicity categories have been combined due to potential small sample size. For age group, should the models fail to converge due to small cell size, age categories may

be further collapsed. For all subgroup models, should the models fail to converge, NA or not assessable or similar will be displayed.

## 9. SAFETY EVALUATION

#### 9.1 Overview of Safety Analysis Methods

Safety analyses will be carried out for the Safety Population. Subjects who do not complete the study, for whatever reason, will have all available data up until the time of termination included in the analyses. Allowable windows for each study visit are laid out in the Schedule of Events in Section 18.1. Assessments that occur outside of the allowable window for each study visit will be flagged as protocol deviations, but will be used in all safety analyses. In general, all data will be associated with the nominal study visit for which it was collected. Repeat assessments and unscheduled visits will be included in study listings, but will not be used in place of nominal timepoint data. It is not expected that there will be multiple measurements that occur within the same assessment time window. Should that occur, the closest measurement will be used in the analysis; an earlier measure will be used in case of a tie. No formal hypothesis testing will be performed.

#### 9.2 Adverse Events

Treatment-emergent adverse events (TEAEs) are defined as those adverse events (AEs) with onset during or after the first dose of study drug or existing events that worsened after the first dose during the study. Treatment-emergent AEs will be summarized by treatment group and severity.

Partial or completely missing AE start dates will be imputed as follows:

- 1. If the year and month are known:
  - a. If the year and month are the same as the year and month of the treatment start date, impute to treatment start date.
  - b. Otherwise, use the 1st of the month.
- 2. If only the year is known:
  - a. If the year is the same as the year of treatment start date, impute to treatment start date.
  - b. Otherwise, impute to January 1st of that year.
- 3. If the date is completely missing, impute to treatment start date.

Partial or completely missing AE end dates will be imputed in the same manner, with end of treatment date or end of study replacing treatment start date in the algorithm.

AE listings will display the imputed dates.

Verbatim terms on case report forms will be mapped to preferred terms and system organ classes using the latest version of MedDRA.

At Visits 5, 6, 7, 8, 9, 12 (EOT), and 13 (Follow-up), treatment-emergent adverse events (TEAEs) in the Safety Population will be summarized by severity in the following tables: all reported TEAEs, all SAEs, all treatment-related SAEs, treatment-related TEAEs, severe TEAEs, TEAEs leading to dose interruption, TEAEs leading to study discontinuation, TEAEs of special interest, and anticholinergic TEAEs. Additionally, local site reaction TEAEs will be summarized in the Safety Population by severity at Visits 5, 6, 7, 8, 9, 12 (EOT), and Visit 13 (Follow-up). Local site reaction TEAEs are defined as AEs coded to the system organ class of general disorders and administration site conditions and, at a minimum, the following preferred terms:

- Application site pruritus
- Application site pain
- Application site irritation
- Application site dermatitis
- Application site rash
- Application site erythema
- Application site discolouration
- Application site dryness
- Application site exfoliation
- Application site reaction
- Application site warmth

Each of the above tables will be produced for cumulative TEAEs up to the current visit reported by all Safety Population subjects (including those absent from the current visit). At each of the visits, each of the above tables will summarize the subject incidence (frequency count and %) for the specified TEAE, mapped to MedDRA System Organ Class and Preferred Term, according to the highest severity reported. Subjects with only unknown severity for a TEAE will be counted under the severity unknown category.

Summaries that are displayed by system organ class and preferred terms will be ordered by descending incidence of system organ class in the total column and preferred term within each system organ class. The total column will not be displayed and will only be used for sorting. TEAEs of special interest include the following:

- Vision blurred
- Mydriasis (unilateral or bilateral)
- Urinary hesitation

An overall TEAE summary table by treatment group with the total number of TEAEs and the number and percentage of subjects with at least one of the following will be presented: TEAE, serious TEAE, treatment-related TEAE, treatment-related serious TEAE, severe TEAE, TEAE leading to dose interruption, TEAE leading to study discontinuation, TEAEs of special interest, anticholinergic TEAEs, anticholinergic TEAEs leading to study discontinuation, local site reaction TEAEs, local site reaction TEAEs leading to study discontinuation. The overall summary table will also display the number and percent of subject deaths, should any deaths occur.

The number of subjects with study discontinuations due to TEAEs, the number of subjects with study discontinuations due to anticholinergic TEAEs, and the number of subjects with study discontinuations due to AESIs will be plotted as a bar chart versus time on treatment. Time on treatment is defined as the earlier of treatment end date or study discontinuation date – treatment start date + 1. Time on treatment will be displayed in categories of 0 to 2 weeks, >2 to 4 weeks, >4 to 6 weeks. Weeks are defined as 7 days. The follow-up visit is excluded.

The number of treatment-related TEAEs and the number of local site reaction TEAEs will be plotted versus time on treatment. The number of subjects with a treatment-related TEAE and the number of subjects with a local site reaction TEAE will be plotted versus time. Time for these plots will be displayed as weeks 1-8 which includes the follow-up visit.

Adverse event data will be presented in data listings by subject, treatment group, and event. SAEs, TEAEs leading to study discontinuation, TEAEs of special interest, and anticholinergic TEAEs will be presented in separate data listings. Death is not expected. However, should death occur on study, the event will be reported with detailed narratives.

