7.2 Visit-Specific Procedures

7.2.1 Visit 1: Screening (Days -31 to 0)

Written informed consent must be obtained prior to any study-related procedures. Potential subjects will be screened within 45 days prior to Visit 4 (Rescreening/Baseline) to assess their eligibility to enter the study. Only eligible subjects with axillary hyperhidrosis will be enrolled.

After informed consent is obtained, the following procedures will be performed:

- Collect and review subject medical history and demographics.
- Assess inclusion/exclusion criteria.
- Subject to complete the GSP assessment.
 - o GSP assessments for all visits will be conducted from 7:00 am to 11:00 am.
 - o One 5-minute GSP assessment will be conducted for each axilla.
 - o Refer to Appendix 1 for instructions and requirements of sample collection and handling.
- Subject to complete the HDSM-Ax assessment.
 - o Five multi-part questions and PGI-S question (administered as Question #6 at the end of the HDSM-Ax questionnaire) to be completed by the subject prior to other assessments.
 - o Refer to Appendix 2 (HDSM-Ax) and Appendix 3 (HDSM-Ax Child)
- Perform UPT if applicable (FOCBP only). If positive, the subject shall be screen failed.
- Collect samples for laboratory assessments (hematology, chemistry, and urinalysis) (see Section 8.1.3).
- Review concomitant medications/treatments and assess for washouts.
- Provide subject with the Sponsor-provided non-antiperspirant deodorant. Resupply as needed throughout subject study participation.
- Schedule the subject to return for Visit 2 (GSP1) after any washout has been completed; must be within 31 days of Visit 1 (Screening).

In the event a subject does not satisfy the sweat production eligibility (Inclusion criterion 2b) at the Screening Visit but is otherwise eligible to continue (i.e., satisfies all other eligibility requirements including HDSM-Ax severity but may still require a washout), the Screening GSP may be retested once during the screening period at the discretion of the Investigator:

- Retest must occur within the 31 days from Screening (Visit 1) and must occur prior to GSP1 (Visit 2).
- HDSM-Ax must also be completed at the time of the Screening GSP retest.
- If subject does not meet inclusion based on GSP and HDSM-Ax results at the time of the retest, the subject shall be screen failed and may not be rescreened.

The subject shall be reminded that, on the day of each clinic study visit:

- Showering in the morning is permissible.

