9.2 Adverse Events

9.2.1 Definitions of Adverse Events

According to 21 CFR Parts 312.32 and 320.32 (IND Safety Reporting, Applicability of Requirements Regarding an "Investigational New Drug Application"), Food and Drug Administration (FDA) Guidance for Industry (Investigational New Drug Safety Reporting Requirements for Human Drug and Biological Products and Safety Reporting Requirements for Bioavailability and Bioequivalence Studies in Humans) (Federal Register/Vol. 75, No. 188/September 29, 2010) and International Council on Harmonisation (ICH) E2A (Clinical Safety and Data Management: Definitions and Standards for Expedited Reporting):

An adverse event (AE) means any untoward medical occurrence associated with the use of a drug in humans, whether or not considered drug related.

A suspected adverse reaction (SAR) means any AE for which there is a reasonable possibility that the drug caused the AE.

The following information should be considered when determining whether or not to classify a test result, medical condition, or other incident as an AE:

Adverse events will be recorded from the time of informed consent.

Abnormal laboratory values should not generally be recorded as AEs unless an intervention is required, the laboratory abnormality results in an SAE, the lab abnormality results in study termination or interruption/discontinuation of study treatment, or the lab abnormality is associated with clinical signs or symptoms. When recording an AE resulting from a laboratory abnormality, the resulting medical condition rather than the abnormality itself should be recorded (e.g., record "anemia" rather than "low hemoglobin").

Complications that occur in association with a protocol-mandated intervention (e.g., invasive procedures such as biopsies) should be recorded as AEs.

Whenever possible, the Investigator should group signs or symptoms that constitute a single diagnosis under a single event term. For example, cough, rhinitis, and sneezing might be grouped together as "upper respiratory tract infection." If possible, abnormal laboratory results that meet the definition of an AE (see above) should be reported as a clinical diagnosis rather than the abnormal value itself (e.g., "anemia" rather than "decreased blood count").

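### SAP 9.2 sets partial or missing AE start dates to the first-dose date without checking the end date, so an AE recorded as over before dosing becomes treatment-emergent

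*SAP*

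**What the plan says.** SAP 9.2 has three branches that move an AE start to the first-dose date:

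- Rule 1a, year and month known: "If the year and month are the same as the year and month of the treatment start date, impute to treatment start date."
- Rule 2a, only the year known: "If the year is the same as the year of treatment start date, impute to treatment start date."
- Rule 3, nothing known: "If the date is completely missing, impute to treatment start date."

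In the other branches the start becomes the first of the recorded month, or 1 January of the recorded year. For end dates: "Partial or completely missing AE end dates will be imputed in the same manner, with end of treatment date or end of study replacing treatment" (what is replaced is the first-dose reference date). That sentence acts only on partial or missing end dates, so a complete end date stays as recorded. TEAE status rests on the timing of onset or worsening: "adverse events (AEs) with onset during or after the first dose of study drug or existing events that worsened after the first dose during the" (that is, while in the trial).

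On collection, Protocol 9.2.1 states: "Adverse events will be recorded from the time of informed consent." Protocol 7.2.1 gives the length of the pre-dose period: "Potential subjects will be screened within 45 days prior to Visit 4." Protocol 9.2.1.2 has both the start and the resolution date documented for every AE. SAP 9.5.3.1 sends partial medication dates through the SAP 9.2 algorithm and calls a medication concomitant if it started on or after the first dose.

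**The concern.** Treating an unknown onset as treatment-emergent is sound when the event might have begun after dosing. A recorded end date before first dose rules that out. The SAP does not use this information, although it is collected. It then produces a record in which the AE starts after it ended, and counts a pre-treatment event as a TEAE.

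The TEAE tables in SAP 9.2 are cumulative over Visits 5, 6, 7, 8, 9, 12 and 13. An event wrongly placed on Day 1 therefore enters the all-TEAE table at the first of these visits and stays in all seven, as well as in the overall summary. At stake are the accuracy of absolute TEAE incidence and the logical consistency of the safety data.

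**Working it through.** The documents state no figure for this rule, so there is none to reproduce. The check applies the rules as written.

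**1. Worked cases.** Assumed dates: first dose 18 March 2021, so a 42-day treatment period ends on 28 April 2021.

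| Recorded start | Recorded end | Imputed start | End used | TEAE | Start after end |
|---|---|---|---|---|---|
| March 2021 | 10 March 2021 | 18 March | 10 March | yes | yes |
| 2021 | 10 March 2021 | 18 March | 10 March | yes | yes |
| missing | 10 March 2021 | 18 March | 10 March | yes | yes |
| February 2021 | 10 March 2021 | 1 February | 10 March | no | no |
| March 2021 | March 2021 | 18 March | 1 March | yes | yes |
| 20 March 2021 | March 2021 | 20 March (recorded) | 1 March | yes | yes |

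Rows 1 to 3 are the error: the event was over 18 − 10 = 8 days before its imputed start. Row 4 is handled correctly. In row 5 the end is ambiguous, so calling the event treatment-emergent is acceptable caution. Rows 5 and 6 show a separate inversion from the end-date sentence: a day-missing end outside the reference month goes to the first of its month, which can precede the start.

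**2. Calendar share for a month-only start.** Take every first-dose date in one year, every onset from 1 to 45 days before it, and every end from the onset day to the day before dosing. An onset *b* days before dosing has *b* possible end days, so the number of combinations is 365 × (1 + 2 + … + 45) = 365 × 1,035 = 377,775.

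- Onset falls in the first-dose month in 56,354 combinations, and 56,354 / 377,775 = 14.9%.
- All 56,354 become TEAEs with a start after the end.
- Counting onset days alone, 32.7% of the 45-day window falls in the first-dose month. The 14.9% is lower because onsets further from dosing have more possible end days and so weigh more.
- If the start goes to the first of the recorded month whenever the known end precedes first dose, the 56,354 fall to 0. AEs ending on or after first dose keep the SAP's assignment.

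Both shares treat all calendar combinations as equally likely. They are not expected event counts.

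**3. Medications.** Under SAP 9.5.3.1, a drug stopped before first dose whose start is recorded only as the first-dose month, only as the first-dose year, or not at all receives the first-dose date as its start. It is then classed as concomitant, although it was never taken on study treatment.

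**4. Search for a safeguard.** Neither document requires a start date to be on or before the end date, and neither exempts events that resolved before dosing.

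**The case against.** The strongest objection is that the error needs several things at once: an AE that begins after consent, ends before first dose, has a usable end date, and lacks a start precise enough to escape the three rules. AEs are reviewed at Visits 2, 3 and 4, with Visits 2 and 3 within 14 days of Visit 4, and Protocol 10 puts data clarification before database lock. A year-only or missing start is least plausible for an event that began within about six weeks. SAP 9.1 plans no formal safety testing, and the rule treats both arms alike. An investigator is also unlikely to call an event related to study drug when it had resolved before dosing. All of this stands, and it limits the size. It does not make the rule's result correct.

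Four stronger inferences are tempting, and the documents do not support them:

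- **The listings conceal the collected dates.** SAP 9.2 says "AE listings will display the imputed dates", but not that they replace the collected ones. SAP 3.1 says data collected under the protocol will be listed, and the listing specifications are in a separate document.
- **Negative AE durations will be reported.** No AE-duration output is planned. The duration in SAP 9.2.1 is of treatment interruption and uses exposure dates.
- **Events will drop out of Listing 16.2.7.4.** Only its title, on screening-period AEs, is given. Whether membership depends on imputed dates is not stated.
- **Nearly every screening AE with a year-only or missing start is misclassified.** That would include events continuing past first dose, for which the rule is ordinary caution.

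**Conclusion.** The point holds within a narrow boundary. For an AE whose recorded end date precedes first dose, rules 1a, 2a and 3 give a result that the data contradict: a treatment-emergent event that starts after it ended. This is a stated rule with a wrong output, not missing detail.

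The effect is probably small. The documents do not give the number of affected AEs. It depends on how many pre-dose AEs have partial start dates, and the calendar shares above do not estimate that. Because the rule is the same in both arms, the main effect is some inflation of absolute TEAE counts, together with impossible date pairs. The co-primary and secondary efficacy analyses are untouched. The rule needs no change for AEs ongoing at first dose, ending after it, or with an end date that could fall on either side.

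**What to change.** Before database lock, amend SAP 9.2 as follows.

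1. **Rules 1a, 2a and 3.** Add: *unless the recorded end date (complete, or partial but necessarily before first dose) precedes first dose; then impute the start to the earliest date consistent with the recorded part, not after the end date, and do not classify the AE as treatment-emergent.* Test this on the recorded end date, not the imputed one. In row 5 of the table the imputed end is 1 March although the event may have ended on 31 March. A completely missing start has no recorded part, so name a floor; the consent date would serve, since AE collection begins there.
2. **End-date sentence.** Add: *an imputed end date may not precede the start date; if it would, set it to the start date.* This removes the inversions in rows 5 and 6, which the first change does not reach.
3. **SAP 9.5.3.1.** Apply the same conditions to medications, so that a drug stopped before first dose is not classed as concomitant.
4. **Optional.** Flag imputed dates in the listings.

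The cost is a few sentences in the SAP and two conditions in the derivation code. No new data are needed.

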Safety analysis will be performed by treatment received for the Safety Population. Treatment-emergent adverse event (TEAE) descriptions will be mapped to standard terms, i.e., Medical Dictionary for Regulatory Activities (MedDRA) system organ class and preferred term. At each post-baseline visit, the number and proportion of subjects reporting any given TEAE will be tabulated cumulatively by severity; each subject will be counted only once according to the worst severity reported up to the current visit. Separate tables will be constructed for (a) all reported TEAEs, (b) protocol treatment-related TEAEs, (c) serious TEAEs, (d) TEAEs leading to protocol treatment discontinuation, (e) protocol treatment-related serious TEAEs, (f) severe TEAEs, (g) TEAEs leading to dose interruption, (h) TEAEs of special interest, and (i) anticholinergic TEAEs.

At each visit, local tolerability assessments will be descriptively summarized by severity. An overall summary table will also be presented with subject incidences tabulated according to the worst severity experienced while on study. In addition, at each post-baseline visit, local tolerability will be summarized as cumulative shift tables versus baseline. Subject counts for each symptom will be cross-tabulated with baseline severity according to the maximum post-baseline severity reported for either axilla up to the current visit.

Laboratory parameters will be descriptively summarized (mean, standard deviation, median, minimum, maximum) for values obtained at Visit 1 and Visit 12. Whereas, vital signs will be summarized in a similar manner at each visit.

Sample Size and Power Estimation

Sample size estimation was performed for the co-primary efficacy endpoints based on the results of a Phase 2b study (BBI-4000-CL-203):

- HDSM-Ax-7 responder analysis: 2-point improvement response rates of 29.8% and 53.7% were assumed for the vehicle and sofpironium bromide gel, 15% arms, respectively. The power is 0.95 with 116 subjects per arm and a total of 232 subjects.
- GSP: using rank transformed GSP data for change from baseline to EOT, a difference of 16.6 in mean ranks between the vehicle and sofpironium bromide gel, 15% arms, with a pooled standard deviation of approximately 39.5, was used for this purpose. Normal approximation yielded a sample size estimate of 296 subjects for the study, 148 each arm, in order to achieve 0.95 power for the GSP coprimary endpoint.

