Not related	An event almost certainly caused by concurrent/underlying illness, other drug, procedure, or
	other causes.

Outcome

Each AE will be characterized according to the outcomes described in the following table:

Outcome	Description
Recovered/Resolved	The subject has fully recovered from the event with no observable residual effects.
Recovering/Resolving	The effects of the event are improving, or events have stabilized (are constant and not expected to improve or worsen) but have not returned to baseline.
Not recovered/Not Resolved	The effects of the event are still present and changing. The event is not considered stabilized or resolved.
Recovered/Resolved with Sequelae	The subject has fully recovered from the event with some observable residual effects.
Fatal	The event was the primary cause of death (may or may not be the immediate cause of death).
Unknown	The event outcome is unknown.

Death is an outcome of an event and not an event *per se*. Sudden death or death due to unexplainable cause(s) is to be reported, but follow-up will be pursued until cause of death is determined.

Action Taken with Study Drug

Action taken with study drug in relation to each adverse event will be characterized as follows:

- None
- Drug withdrawn
- Drug interrupted
- Dose reduction
- Unknown
- Not applicable
- Other (specify on eCRF)

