10.4 Safety Analyses

Safety assessments of interest are local tolerability assessments, AEs, laboratory evaluations, and vital signs.

Safety analysis will be performed by treatment received for the Safety Population. Treatment-emergent adverse event descriptions will be mapped to standard terms, i.e., Medical Dictionary for Regulatory Activities (MedDRA) system organ class and preferred term. At each post-baseline visit, the number and proportion of subjects reporting any given TEAE will be tabulated cumulatively by severity; each subject will be counted only once according to the worst severity reported up to the current visit. Separate tables will be constructed for (a) all reported TEAEs, (b) protocol treatment-related TEAEs, (c) serious TEAEs, (d) TEAEs leading to protocol treatment discontinuation (e) protocol treatment-related serious TEAEs, (f) severe TEAEs, (g) TEAEs leading to dose interruption, (h) TEAEs of special interest, and (i) anticholinergic TEAEs.

At each visit, local tolerability assessments will be descriptively summarized by severity. For any symptoms, subject severity is the worst severity of the two axillae.

An overall summary table will also be presented with subject incidences tabulated according to the worst severity experienced while on study. In addition, at each post-baseline visit, local tolerability will be summarized as cumulative shift tables versus baseline. Subject counts for each symptom will be cross-tabulated with baseline severity according to the maximum post-baseline severity reported for either axilla up to the current visit.

Laboratory parameters will be descriptively summarized (mean, standard deviation, median, minimum, maximum) for values obtained at Visit 1 and Visit 12. Whereas, vital signs will be summarized in a similar manner at each visit.

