# 9.2.1 Allergic Contact Dermatitis

Allergic contact dermatitis (ACD), as an AE, may manifest as moderate to severe pruritus and moderate to severe erythema with or without vesicles or bullae.

In the case of a suspected AE of ACD, the Medical Monitor should be contacted to discuss the case and the following steps should be taken at the discretion of the Investigator: 1) assigned treatment should be withheld, 2) the AE of ACD documented, 3) any necessary concomitant treatment should be administered, which can include topical corticosteroids.

Once the AE of ACD is resolved in the opinion of the Investigator, any concomitant therapy for this AE should be stopped, and the assigned treatment should be restarted after discussion with the Medical Monitor (i.e., re-challenge exposure). If there is a recurrence, ACD is confirmed and should be documented as an AE that is related to the assigned study treatment.

Confirmed ACD cases are defined as cases which led to recurrence of ACD event following treatment restart. Suspected ACD cases are those events with "Suspected Allergic Contact Dermatitis" checked on the AE eCRF page. The following parameters will be summarized with descriptive statistics by treatment group to characterize instances of ACD:

- Number and percentage of subjects with treatment-emergent ACD events by severity
- Number and percentage of subjects with treatment-emergent ACD events leading to treatment discontinuation by severity

- Number and percentage of subjects who restarted treatment after the ACD event and later discontinued treatment. These will be confirmed ACD events.
- Time to first confirmed ACD event in days defined as: start date of the ACD event treatment start date + 1.
- Time to first treatment interruption due to confirmed ACD event in days defined as: last exposure date prior to ACD event leading to interruption treatment start date + 1.
- Duration of treatment interruption in days defined as: date of first exposure after end of ACD event - date of last exposure prior to ACD event leading to interruption + 1. If the ACD event is ongoing, either the treatment discontinuation date or first available exposure date after the start of the event will be used to calculate duration. If subject experienced more than one interruption due to ACD, durations of interruptions will be summed.
- Time to treatment discontinuation in days defined as: date of treatment discontinuation date of treatment start + 1.

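### The SAP replaces the protocol's table of TEAEs leading to treatment discontinuation with one of TEAEs leading to study discontinuation, and does not record the change

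*SAP*

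**What the plan says.** Protocol Section 10.4 lists nine separate TEAE tables, (a) to (i). Table (d) is "TEAEs leading to protocol treatment discontinuation"; the synopsis gives the same item. It stands apart from (g), which covers dose interruption.

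SAP Section 9.2 sets out the corresponding by-visit tables. Where the protocol has item (d), the SAP list reads "TEAEs leading to dose interruption, TEAEs leading to study discontinuation". The overall TEAE summary uses the same terms: "TEAE leading to dose interruption, TEAE leading to study discontinuation, TEAEs of special interest".

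The one place where the SAP summarises the end of treatment because of an adverse event is Section 9.2.1 on allergic contact dermatitis, which asks for the number and percentage of subjects with "treatment-emergent ACD events leading to treatment discontinuation by severity".

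Protocol Section 9.2.1.2 has the action taken with study drug recorded for every adverse event. "Drug withdrawn" is one of its categories, separate from interruption and from dose reduction.

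SAP Section 1 undertakes to document in the SAP, before database lock, any change from the protocol's analyses. SAP Section 13 names two: the mITT population, and the definition and analysis of local site reaction TEAEs.

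**The concern.** Stopping the drug because of an adverse event is a standard measure of tolerability, and the protocol asked for it by name. Leaving the study is a different event. If a subject can stop the gel and still attend visits, a table of study discontinuations does not count that subject, and the reader of the clinical study report cannot see that an adverse event ended treatment.

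The same gap affects the overall-summary rows for anticholinergic and local site reaction TEAEs, which the SAP also words as leading to study discontinuation. The protocol's background section presents these two kinds of event as the expected effects of the drug and its route.

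The substitution is also undocumented, against the SAP's own rule. A reader who compares the report with the protocol would find a specified safety table missing without explanation.

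**Working it through.** The plan gives no figure to reproduce. The check is a comparison of text, followed by a statement of what one affected subject is worth.

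**1. Promised against planned.**

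- Protocol synopsis and Section 10.4: a table of TEAEs leading to discontinuation of treatment.
- SAP 9.2 by-visit tables (Visits 5, 6, 7, 8, 9, 12 and 13; planned Tables 14.3.1.2.7 to 14.3.1.8.7): study discontinuation.
- SAP overall summary (Table 14.3.1.1): study discontinuation for all, anticholinergic and local site reaction TEAEs.
- SAP figures 14.3.1.1.1 to 14.3.1.1.3 and Listing 14.3.2.2: study discontinuation.
- SAP Table 14.3.1.9 (ACD): treatment discontinuation, for ACD events only.
- SAP Section 13: no mention of the substitution.

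No planned TEAE table, figure or separate listing covers treatment discontinuation across all TEAEs.

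**2. Are the two terms interchangeable in these documents?** Four places indicate that they are not.

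- Protocol 9.2.1, on laboratory abnormalities, names study termination and the stopping or interruption of study treatment as separate outcomes.
- Protocol 9.2.1.2 records what was done with the drug for each event, whatever the subject's study status.
- SAP 5.1 counts subjects completing treatment separately from subjects completing the study, and tabulates reasons only for early departure from the study.
- SAP 9.2 defines time on treatment by whichever comes first of the treatment end date and the study discontinuation date, so the two dates can differ.

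**3. One subject traced through the outputs.** Take a subject with a non-ACD TEAE, action recorded as "Drug withdrawn", who goes on attending visits.

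- Dose-interruption tables: absent, because the action is withdrawal and not interruption.
- Study-discontinuation tables, figures and listing: absent, because the subject has not left.
- ACD summary: absent.
- Disposition: counted as not completing treatment, with no reason tabulated.
- All-TEAE tables and Listing 16.2.7.1: present, but the tables do not show that the event ended treatment.

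**4. Size.** Let N be the subjects in an arm, s those who leave the study because of a TEAE (assumed to stop the drug as well), and k those who stop the drug for a TEAE but stay on study. The protocol's table would show (s + k)/N and the SAP's shows s/N, so the difference is k/N. Protocol Section 2 plans 175 per arm, so each such subject is worth 1/175 = 0.57 percentage points. The documents give no value for k. At k = 0 the two tables agree.

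**The case against.** The strongest reply is that subjects who stop the drug but stay on study may hardly exist in this trial. Protocol 7.4 describes discontinuation from the study only. It places inability to tolerate the product among the grounds for leaving the study, and it asks those who leave to complete the Visit 12 evaluations. It sets out no route for staying on study without the drug. Protocol 9.5.1 likewise joins stopping the product to leaving the study when pregnancy is confirmed. SAP 8.2.1.1, in justifying its imputation model, moves from stopping treatment to dropping out as if they were one event. This stands as a limit on size: k may be small or zero. It does not make the terms equivalent, because Protocol 7.4 is permissive and other sections keep the two apart.

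It can also be said that nothing is lost. The SAP promises to list all data collected, the events remain in the all-TEAE tables and the all-AE listing, and a gap between treatment completion and study completion would show in disposition. That is correct. What is missing is a tabulation.

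Three stronger readings are tempting.

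- A reader might infer that subjects will be missed, mostly in the active arm. The documents show only that they could be; no rate or split by arm is given.
- A reader might take the efficacy estimands, which apply whether or not subjects adhere to treatment, as evidence that such subjects are expected. That wording covers any non-adherence, including missed doses, and does not establish that subjects stop the gel for an adverse event and stay. The ACD summary does not establish it either, since ACD has its own withhold-and-restart procedure.
- A reader might conclude that the protocol also promised matching figures and listings. Section 10.4 promises tables; the figures, the overall summary and the discontinuation listing come from the SAP.

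**Conclusion.** The mismatch is certain on the text: the SAP drops a protocol-specified tolerability table, puts a different one in its place and does not say so in Section 13. The consequence is conditional. A non-ACD subject who stops the drug for a TEAE and stays on study could be absent from every discontinuation and interruption summary. How many subjects that describes is unknown, and it may be few or none.

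This rests on two assumptions: that the SAP's label is applied literally, since Section 9.2 does not state which eCRF field identifies an event leading to study discontinuation; and that interruption and withdrawal are coded as the separate categories the protocol lists. The co-primary and secondary efficacy analyses are not affected. The point is worth correcting because the correction is cheap and the table was promised. If the two counts turn out the same, producing the promised table will show it.

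**What to change.** In SAP Section 9.2, add TEAEs leading to treatment discontinuation, identified by the adverse-event action "Drug withdrawn", to the by-visit tables and as a row in the overall TEAE summary. Keep study discontinuation as an additional row, and state which field identifies each. Matching time-on-treatment figures and a listing are optional. If the sponsor prefers to keep only study discontinuation, Section 13 should record the change and justify it.

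The cost is one more set of seven by-visit tables and an added summary row, all from data already on the eCRF. No trial procedure or data collection changes. If the database is already locked, SAP Section 1 allows supplementary analyses that are described in the clinical study report.
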